 - Patients are allowed up to three attempts to meet reversibility criteria, within the screening period (see Section 4.5.2 for details).
 - Specific guidelines for performing and interpreting bronchodilator reversibility testing, including medication-withholding strategies and appropriate dosing of short-acting bronchodilators, will be provided to investigators.
- Uncontrolled asthma during the screening period, defined as an ACQ-5 score ≥ 1.5 and at least one of the following symptoms of asthma that is not controlled according to EPR3 (2007) and GINA (2015) guidelines *during each of 2 consecutive weeks*:
 - Nighttime awakening ≥ 1 time/week
 - Use of short-acting rescue therapy > 2 days/week

- Documented history of at least one asthma exacerbation within 12 months prior to screening while on daily ICS maintenance therapy (same or higher dose as at screening), defined as new or increased asthma symptoms (wheezing, coughing, dyspnea, chest tightness, and/or nighttime awakenings due to these symptoms) that result in one or both of the following:
 - Hospitalization or emergency department, urgent care visit, or urgent unscheduled office visit requiring administration of asthma treatment, such as bronchodilators and/or systemic corticosteroids, in addition to baseline controller medications
 - Treatment with systemic corticosteroids for ≥ 3 days or a long-acting depot corticosteroid preparation with a therapeutic effectiveness of ≥ 3 days
- Demonstrated compliance with required use of the eDiary, defined as documenting asthma controller medication use and answering questions related to asthma symptoms, nighttime awakenings due to asthma, and use of short-acting rescue therapy on 5 of 7 days during each of 2 consecutive weeks during the screening period (see Section 4.5.5.2 and Section 4.5.5.3 for details)
- Demonstrated compliance with required PEFr measurements, defined as measuring PEFr on 5 of 7 days during each of 2 consecutive weeks during the screening period (see Section 4.5.5.1 for details)
- Demonstrated adherence with usual asthma controller medication regimen, defined as patients responding affirmatively that they have taken their asthma controller medications on 5 of 7 days during each of 2 consecutive weeks during the screening period, as recorded in the eDiary
- Demonstration of acceptable inhaler, peak flow meter, and spirometry techniques at screening

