4.5.5.3 Daily Diary Symptom-Related Asthma Assessments

Patients will complete daily diary questions on the eDiary twice a day. The daily diary comprises morning items (to be completed when patients wake up) and evening items (to be completed at bedtime). The eDiary will remind patients when it is time to complete their diary. Details about the specific content are described in Morning Diary Questions and Evening Diary Questions below.

Morning Diary Questions

The morning diary (see [Appendix 4](#)) is comprised of 4 measures:

1. Asthma Daily Symptom Diary: Nighttime Symptoms

The Asthma Daily Symptom Diary (ADSD) (nighttime symptoms) includes 7 items that allow patients to rate the severity of their nighttime asthma symptoms since they went to bed the previous night on an 11-point scale ranging from 0 (none) to 10 (as bad as you can imagine).

A single item is used to assess each of the following concepts:

- Breathing
- Wheezing
- Shortness of breath
- Chest tightness
- Chest pain
- Cough
- Feeling of mucus in the chest

The ADSD nighttime symptom questions will be administered on 3 non-consecutive days during screening, run-in visit, randomization visit, daily for 7 days prior to Week 26, and daily for 7 days prior to Week 54.

2. Nighttime awakening due to asthma

Patients will respond to a single item asking whether they woke up because of their asthma symptoms (yes/no). The nighttime awakening due to asthma question will be administered every morning beginning at screening through Week 54.

3. Short acting symptom relief medication (short-acting rescue therapy)

Patients will be asked whether they used short-acting rescue medication to relieve their asthma symptoms during the night (yes/no). If “yes,” they will be asked whether they used an inhaler and whether they used a nebulizer (“breathing machine”) with instruction to choose “all that apply.” The short-acting symptom relief medication question will be administered every morning beginning at screening through Week 54.

4. Patient Global Impression of Severity

The Patient Global Impression of Severity (PGIS) completed in the morning diary asks patients to rate their nighttime asthma symptoms on an 11-point scale ranging from 0 (no symptoms) to 10 (as bad as you can imagine). The morning diary PGIS will be administered 4 times: at the run-in visit, the randomization visit, one day prior to Week 26 visit, and one day prior to Week 54 visit.

Evening Diary Questions

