4.2 DEFINITION OF BASELINE

Baseline is defined as the last available pre-treatment value taken on or before the day of randomization (Week 2 visit) for all assessments, with the exception of the following efficacy endpoints: patient-reported use of short-acting rescue therapy, and patient-reported daytime asthma symptom severity as measured by Asthma Daily Symptom Diary (ADSD). For these outcome measures, details for derivation of baseline values can be found in [Section 4.5.2](#).

Baseline measurements will be used for the summary of demographic characteristics, as well as for all change-from-baseline analyses of efficacy, safety, and PD endpoints (including change from baseline in FEV1, CGIC, blood eosinophil count, and FeNO, and improvement from baseline in AQLQ(S), ACQ-5, SGRQ, ACQ-7).

For endpoints that are defined in terms of change from baseline or improvement from baseline, patients who do not have a baseline measurement will be excluded from the analyses.

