The proportion of patients who achieve a clinically meaningful improvement in AQLQ(S) (improvement of ≥ 0.5 points from baseline) at Week 54 will be summarized by treatment group and timepoint. AQLQ(S) at randomization visit (Week 2) will be used as the baseline AQLQ(S) score. A logistic regression model, with terms for treatment group, baseline AQLQ(S), and the baseline covariates described in Section 4.5 will be used to compare MSTT1041A with placebo. For patients without a Week 54 assessment of AQLQ(S), the Week 26 score will be used. Patients without a post-randomization assessment (Week 26 or Week 54) will be excluded from the analysis. Point estimates, 95% CIs, and p-values for the treatment difference (MSTT1041A vs. placebo) will be calculated for each MSTT1041A dose level.

Considering each dose level separately, if a statistically significant difference between MSTT1041A and placebo is observed at Week 54, then a test for significance will be performed at Week 26. This procedure will be used to determine the earliest timepoint at which significance is observed (comparing MSTT1041A with placebo), and considered the time of onset of sustained AQLQ(S) improvement.

Asthma Control Questionnaire

Asthma control, as measured by the ACQ, will be assessed by asking patients to recall their experience with asthma during the previous week. The full ACQ consists of seven questions: five questions related to symptoms (i.e., nighttime awakening, asthma symptoms upon awakening in the morning, activity limitation, shortness of breath, and wheezing frequency), one question about use of short-acting rescue therapy, and one question about FEV₁ (to be completed by site staff). The items are scored on a scale ranging from 0 (totally controlled) to 6 (extremely poorly controlled). The items are equally weighted. For the ACQ, higher scores indicate worse control, and 0.5 points is considered the MID. The ACQ can be scored two ways: 1) the mean of the five symptom-related items (ACQ-5); or 2) the mean of all 7 items (ACQ-7).

The proportion of patients who achieve a clinically meaningful improvement in asthma control based on the ACQ-5 (decrease of ≥ 0.5 points from baseline) will be analyzed using the same methodology as described for achievement of improvement from baseline at Week 54 in AQLQ(S). ACQ-5 at randomization visit (Week 2) will be used as the baseline ACQ-5 score.

Asthma Rescue Medication Use

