The absolute change from baseline in the proportion of days with asthma rescue medication use will be summarized by treatment arm and timepoint. The absolute difference in mean change in proportion of days of rescue medication use from randomization at Week 54 between each treatment arm and the placebo arm will be estimated on the basis of an MMRM analysis. The model will use absolute change from baseline as the response variable and include terms for treatment arm, study visit, treatment arm by study visit interaction, baseline asthma rescue medication use (as a continuous variable) as well as its interaction with study visit, and the baseline covariates described in Section 4.5. Study visit will be included as a categorical variable. An unstructured covariance matrix will be specified to model the within-subject errors. Point estimates, 95% CIs, and p-values for the treatment difference (MSTT1041A vs. placebo) will be calculated for each MSTT1041A dose level based on the model for all study visits including Week 54.

Asthma-Related Nighttime Awakenings

Nighttime awakenings, as recorded each morning in the patient's daily e-Diary, will be used for analysis. For each patient, the proportion of weeks without a nighttime

awakening from baseline through Week 54 will be calculated. The randomization visit (Week 2) will be used as baseline.

From the randomization visit, the subsequent weeks will be counted by a 7-day window until Week 54 is reached. For each 1-week period after randomization visit, if there are 4 or more morning diaries with missing entries, the 1-week period is considered a non-compliant week and the corresponding value will be considered as missing. These missing values will not be imputed, and these missing weeks will not be included in the denominator when calculating the proportion of weeks. However, if there are >3 morning diaries with missing entries during a 1-week period but one of the available entries for the 1-week period reports a nighttime awakening, this 1-week period will be included in the calculation.

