The proportion of weeks without a nighttime awakening due to asthma will be summarized by treatment arm. The absolute difference in mean proportion between each MSTT1041A dose level and the placebo arm will be estimated on the basis of an analysis of variance model. The model will use the proportion of weeks without a nighttime awakening due to asthma as the response variable and include terms for treatment arm and the baseline covariates described in Section 4.5. Point estimates, 95% CIs, and p-values for the treatment difference (MSTT1041A vs. placebo) will be calculated for each MSTT1041A dose level.

Daytime Asthma Symptom Severity

Daytime asthma symptom severity will be assessed by patient ratings of asthma symptoms each evening, as recorded in the ADSD on their e-Diary.

The daily daytime symptom scores are calculated each day as an average of the six core evening diary symptoms: difficulty breathing, wheezing, shortness of breath, chest tightness, chest pain and cough. Each question is scored from the scale of 0 to 10, in which higher scores indicate worse symptoms. The daytime symptom score for each timepoint is then calculated as a weekly average of the 7 individual average daily scores. Daily scores will only be calculated if data for 4 or more items per day are available.

Daily scores will be averaged over the previous week prior to each scheduled visit (i.e., 7 days prior to Week 54 visit). For each week after randomization visit, if there are >3 days with missing scores out of the 7 days, the week is considered a non-compliant week and the average score for the week will be considered as missing. These missing values will not be imputed but will be handled directly by the MMRM model.

The baseline value will be derived based on a 2-week screening period prior to the Week 0 visit. Patients must have two consecutive compliant weeks during screening to have a baseline score calculated. During screening, a patient is compliant in a week if they have at least 5 of 7 days of non-missing scores. The baseline score will first be calculated using the two consecutive screening compliant weeks prior to the run-in visit.

However, if the condition of two consecutive screening compliant weeks does not hold in the 14 days prior to the run-in visit, the window will be shifted back by 7 days until a period of two consecutive screening compliant weeks is identified. Patients without a 'valid' baseline score will be excluded from the analysis.

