The absolute change from baseline in daytime symptom severity scores will be summarized by treatment arm and timepoint. The absolute difference in mean change in daytime symptom severity scores from baseline at Week 54 between each treatment arm and the placebo arm will be estimated on the basis of an MMRM analysis. The model will use absolute change from baseline as the response variable and include terms for treatment arm, study visit, treatment arm by study visit interaction, baseline symptom score as well as its interaction with study visit, and the baseline covariates described in Section 4.5. Study visit will be included as a categorical variable. An unstructured covariance matrix will be specified to model the within-subject errors. Point estimates, 95% CIs, and p-values for the treatment difference (MSTT1041A vs. placebo) will be calculated for each MSTT1041A dose level based on the model for all study visits including Week 54.

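### The nighttime-awakening endpoint is analysed without the patient's own screening awakenings, which the diary already records: the test stays valid, but precision is given up

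*SAP*

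**What the plan says.** For the nighttime-awakening endpoint, SAP 4.5.2 specifies an analysis of variance: "The model will use the proportion of weeks without a nighttime awakening due to asthma as the response variable". The only terms are treatment arm and the SAP 4.5 covariates: eosinophil level, exacerbation history, inhaled corticosteroid dose and geographic region.

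The same subsection states "The randomization visit (Week 2) will be used as baseline". In context this fixes where the 7-day windows start counting; no pre-treatment awakening score is derived from it. SAP 4.2 gives the general rule, "Baseline is defined as the last available pre-treatment value taken on or before the day of randomization (Week 2 visit) for all assessments", and exempts only rescue use and daytime symptom severity, which have their own screening-window derivations.

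The pre-treatment data are collected. Protocol 4.5.5.3 says "The nighttime awakening due to asthma question will be administered every morning beginning at screening through Week 54". The run-in inclusion criteria (Protocol 4.1.1.1) require diary answers on "nighttime awakenings due to asthma, and use of short-acting rescue therapy on 5 of 7 days during each of 2 consecutive weeks".

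Elsewhere in SAP 4.5.2 the models carry the patient's own starting value:

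- AQLQ(S), with ACQ-5 by the same method: "A logistic regression model, with terms for treatment group, baseline AQLQ(S), and the baseline covariates described in Section 4.5 will be used".
- Rescue medication: "baseline asthma rescue medication use (as a continuous variable) as well as its interaction with study visit".
- Daytime symptoms: "baseline symptom score as well as its interaction with study visit".
- FEV₁: baseline FEV₁ and its interaction with visit.

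**The concern.** A patient's own pre-treatment level is a natural candidate to predict a symptom frequency averaged over the following year. Here it is collected, close to complete by design, and left out of the model. The remaining secondary endpoint, time to first exacerbation, at least adjusts for exacerbation history. Nighttime awakening is therefore the only secondary endpoint whose model contains no pre-treatment measure of the outcome itself.

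The entry criteria leave room for wide differences at the start. Weekly awakening and rescue use on more than 2 days a week are alternatives, so patients who wake often and patients who qualify on rescue use alone can both enrol. Randomization is not stratified on awakenings, so nothing in the design or the model absorbs a chance imbalance.

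If screening awakenings predict later ones, the confidence intervals are wider and the power lower than the collected data allow. This is secondary endpoint 5 in the fixed sequence. If testing reaches it, a miss here also closes formal testing of endpoints 6 and 7.

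**Working it through.** **No plan figure to reproduce.** The documents state no power, standard deviation or effect size for this endpoint, and no correlation between screening and later awakenings.

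**Inputs from the documents.** 502 patients in four arms (SAP 2.2); two-sided 5% level (SAP 4.5); model terms from SAP 4.5 and 4.5.2.

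**Assumed inputs.** The partial correlation r of screening awakenings with the outcome, given the SAP 4.5 covariates, shown from 0 to 0.7; and 80% power under the planned model as a reference point.

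**Formulas.**

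- Variance factor: 1 − r²
- Confidence interval width factor: √(1 − r²)
- Equivalent extra patients: 1/(1 − r²) − 1
- Power: Φ[(1.960 + 0.842)/√(1 − r²) − 1.960]

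For example, at r = 0.5: √0.75 = 0.866; 2.802/0.866 = 3.235; 3.235 − 1.960 = 1.275; Φ(1.275) = 89.9%.

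| r | Variance factor | CI width factor | Equivalent extra patients | Power |
|---|---|---|---|---|
| 0 | 1.00 | 1.000 | 0% | 80% |
| 0.2 | 0.96 | 0.980 | 4.2% | 81.6% |
| 0.3 | 0.91 | 0.954 | 9.9% | 83.6% |
| 0.5 | 0.75 | 0.866 | 33.3% | 89.9% |
| 0.7 | 0.51 | 0.714 | 96.1% | 97.5% |

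**Cost of the term.** The planned model has 1 (intercept) + 3 (arm) + 2 (eosinophils) + 1 (exacerbations) + 1 (corticosteroid dose) + 3 (region) = 11 parameters. If all 502 patients contribute, residual degrees of freedom go from 502 − 11 = 491 to 490. The expected variance penalty is about 1/488 = 0.2%, so the covariate breaks even at r ≈ √0.002 = 0.045.

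**Simulation checks.**

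1. Normal outcome, 502 patients, four arms, seven other covariate columns, 6,000 runs per setting. Type I error was 4.8% to 5.2% for both models. Power was 78.7% to 79.8% without the covariate. With it, power was 79.1%, 80.2%, 82.2%, 89.1% and 97.5% at r = 0, 0.2, 0.3, 0.5 and 0.7.
2. A diary-like simulation: 125 patients per arm, 14 screening nights, 52 weeks, 15% early dropout, 2,000 runs per null scenario. Type I error was 4.5% to 5.8% for the planned model and 4.4% to 5.6% with the covariate (Monte Carlo error about 0.5 points). Screening-to-outcome correlations of about 0.30, 0.46 and 0.60 in absolute value gave standard error ratios of about 0.95, 0.89 and 0.80, close to √(1 − r²). With an illustrative effect, power rose from 65–70% to 70–75%, 78–80% and 85–87%.

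**The case against.** The strongest reply is that nothing here is wrong. The endpoint is a level over 52 weeks, not a change, so it needs no baseline score to exist, and its response, model and missing-week rule are fully specified. That stands as far as it goes: the omission is neither a contradiction nor a source of bias. It does not justify leaving the covariate out. A baseline term raises precision whether the response is a level or a change, and the SAP includes one in its logistic models for AQLQ(S) and ACQ-5.

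The size rests on an assumed r. This also stands. Screening weeks are used to select patients on awakenings or rescue use, so regression to the mean is plausible, and r relates about 14 nights to a year's average after other covariates. At r = 0.2 the interval narrows by only 2%. The larger gains are conditional, not predicted.

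The effect on the testing sequence is remote. If each endpoint is taken through all three doses before the next, as the SAP 4.5 text reads, 5 × 3 = 15 hypotheses precede endpoint 5 at 490 mg; within a single dose, five precede it. The primary alone is planned at about 80% power for one arm. So the effect on formal testing matters only if the earlier tests succeed. The gain in interval width does not depend on that, because SAP 4.5.2 provides estimates and intervals for every dose.

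Other covariates are possible: the two run-in weeks are also recorded and lie closer to randomization, and a weekly measure would match the outcome's scale. These are reasonable alternatives; they do not make the screening covariate unsound.

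**Conclusion.** The concern holds, as a missed gain in efficiency. The planned model omits a pre-treatment measure of its own outcome that is available for essentially every patient, while the other secondary models adjust for theirs. Omitting it leaves the test unbiased with type I error near 5%. The loss runs from nothing at r = 0, through a 2% wider-than-necessary interval at r = 0.2, to the equivalent of a third more patients at r = 0.5. These figures rest on the assumed r, and the power figures also on the assumed 80% starting point. The change is worth making because its cost is about 0.2% of variance against a gain that may be substantial. The primary endpoint is not affected. The statement that the test stays valid concerns the omitted covariate only, not the handling of non-compliant diary weeks.

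**What to change.** Before unblinding and the 54-week analysis, change the model to an analysis of covariance with one added continuous term: the proportion of nights with an asthma awakening over the two consecutive compliant screening weeks before the run-in visit, using the same window and shift-back rule as rescue use and daytime symptoms.

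In SAP 4.2 and 4.5.2, name this screening covariate separately from the Week 2 visit, which should remain only the start of the weekly windows.

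Do not carry over the rule that excludes patients without a valid baseline. This endpoint can be computed without one, so keep any such patient, for example by using the screening nights available or the covariate mean pooled over all arms.

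The cost is one model degree of freedom and short edits to two SAP sections; no new data are needed. Timing matters, because SAP 1 allows no changes at or after the 54-week analysis.

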4.5.3 Exploratory Efficacy Endpoints

Asthma Exacerbation as Defined in Appendix 5

The incidence of asthma exacerbations, defined as in [Appendix 5](#), will be analyzed with the use of the same methodology as described for the primary endpoint (see Section 4.5.1).

Severe Asthma Exacerbations

The incidence of severe asthma exacerbations, defined as asthma symptoms requiring hospitalization or resulting in death attributed to asthma, will be analyzed with the use of the same methodology as described for the primary endpoint (see Section 4.5.1).

Asthma Exacerbations through Week 70

The incidence of severe asthma exacerbations from randomization through Week 70 will be analyzed with the use of the same methodology as described for the primary endpoint (see Section 4.5.1).

Relative Change in Pre-Bronchodilator Forced Expiratory Volume in 1 Second (Liters)

For each patient and timepoint, the relative change in pre-bronchodilator FEV₁ will be defined as the absolute change from the baseline in FEV₁ (liters) divided by the FEV₁ (liters) at baseline. The relative change in pre-bronchodilator FEV₁ from the baseline will be analyzed using the same methodology as described for the secondary endpoint of absolute change in pre-bronchodilator FEV₁ from baseline to Week 54, except that relative change from baseline will be the response variable.

Pre-Bronchodilator Forced Expiratory Volume in 1 Second (Percentage Predicted)

The absolute change in pre-bronchodilator FEV₁ (percentage predicted) from baseline to Week 54 will be analyzed using the same methodology as described for the secondary endpoint of absolute change in pre-bronchodilator FEV₁ from baseline to Week 54.

Pre-Bronchodilator Forced Expiratory Volume in 1 Second (Liters) at Week 70

The absolute change in pre-bronchodilator FEV₁ from baseline to Week 70 will be analyzed using the same methodology as described for the secondary endpoint of absolute change in pre-bronchodilator FEV₁ from baseline to Week 54.

St. George's Respiratory Questionnaire

The SGRQ is a 50-item respiratory-specific quality-of-life questionnaire initially developed and validated for use in chronic obstructive pulmonary disease. It includes questions that assess the impact of disease on symptoms, activity, and functionality. The symptom scale assesses the severity of respiratory symptoms, the activity scale examines impairment in patient activity as a result of respiratory symptoms, and the impact scale evaluates effects of respiratory symptoms on overall function and well-being. Each scale is scored from 0 to 100, and a total score represents the weighted average of these three components.

Each item in the SGRQ has specific weight (lowest possible weight=0, highest=100). Scores for the three scales and total are calculated using the assigned weights. The numerator and denominator for the total and each scale are comprised of individual item weights, minus specific scale weights. See [Appendix 4](#) for weighting, and numerator/denominator calculation details.

Total and scale scores will be calculated as follows:

$$\text{Total Score} = 100 * ([\sum \text{item weights}] / (\text{maximum total weight}))$$

$$\text{Symptom Score} = 100 * ([\sum \text{item 1,2,3,4,5,6,7,8 weights}] / (\text{maximum symptom total weight}))$$

$$\text{Activity Score} = 100 * ([\sum \text{item 11,15 weights}] / (\text{maximum activity total weight}))$$

$$\text{Impact Score} = 100 * ([\sum \text{item 9,10,12,13,14,16,17 weights}] / (\text{maximum impact total weight}))$$

The maximum number of missing values that can be tolerated for each scale are as follows:

- Symptoms: 2
- Activity: 4
- Impacts: 6

Missing item weights are subtracted from each scale's total weight for calculating that scale's score.

The proportion of patients who achieve a clinically meaningful improvement in the SGRQ (defined as a decrease of ≥ 4 points from baseline) will be analyzed using the same methodology as described for the secondary endpoint of achievement of improvement from baseline to Week 54 in AQLQ(S). SGRQ at randomization visit (Week 2) will be used as the baseline score.

Asthma Control Questionnaire

The achievement of improvement from randomization visit in ACQ-7 score at Week 54, defined as a decrease of ≥ 0.5 points, will be analyzed using the same methodology as described for the secondary endpoint of achievement of improvement from baseline to Week 54 in AQLQ(S). ACQ-7 at randomization visit (Week 2) will be used as the baseline score.

Clinician Global Impression of Change

The CGIC is a single-item assessment of the clinician's impression of a patient's change in asthma symptoms since beginning the 52-week double-blind treatment period. Change in asthma symptoms is rated on a 7-point scale ranging from very much worse to very much improved.

CGIC outcomes will be summarized on the basis of the proportion of patients with an outcome at each of the possible levels (i.e., "very much worse" to "very much improved") by treatment arm and timepoint. The proportion of patients with a "very much improved" or "much improved" CGIC score at Week 54 will be compared between each MSTT1041A arm and the placebo arm with the use of a logistic regression model with terms for treatment arm and the baseline covariates as described in Section 4.5. For patients without a Week 54 assessment, the Week 26 assessment will be used. Patients who have missing CGIC scores at both Weeks 26 and 54 will be excluded from analysis.

Biomarker Subgroup Analyses

Details about efficacy analyses by eosinophil and *IL1RL1* genotype subgroups are presented in Section 4.5.6.

